Parameter	Grade 1 Mild	Grade 2 Moderate	Grade 3 Severe	Grade 4 Potentially Life- Threatening
Urinary Tract Obstruction	NA	Signs or symptoms of urinary tract obstruction without hydronephrosis or renal dysfunction	Signs or symptoms of urinary tract obstruction with hydronephrosis or renal dysfunction	Obstruction causing life-threatening consequences

Site Reactions to Injections and Infusions

Parameter	Grade 1 Mild	Grade 2 Moderate	Grade 3 Severe	Grade 4 Potentially Life- Threatening
Injection Site Pain or Tenderness Report only one	Pain or tenderness causing no or minimal limitation of use of limb	Pain or tenderness causing greater than minimal limitation of use of limb	Pain or tenderness causing inability to perform usual social & functional activities	Pain or tenderness causing inability to perform basic self- care function OR Hospitalization indicated
Injection Site Erythema or Redness ¹ Report only one > 15 years of age	2.1 to < 5 cm in diameter	≥5 to <10 cm in max diameter or or ≥25 to < 100 cm2 surface area OR Symptoms causing greater than minimal interference with usual social & functional activities	 ≥10 cm in diameter OR ≥100 cm² surface area OR Phlebitis OR Sterile abscess OR Symptoms causing inability to perform usual social & functional activities 	Potentially life- threatening consequences (eg, abscess, exfoliative dermatitis, necrosis involving dermis or deeper tissue) OR Hospitalization indicated

Parameter	Grade 1 Mild	Grade 2 Moderate	Grade 3 Severe	Grade 4 Potentially Life- Threatening
Injection Site Erythema or Redness ¹ Report only one ≤ 15 years of age	2.1 cm to ≤ 2.5 cm in diameter	> 2.5 cm in diameter with < 50% surface area of the extremity segment involved (eg, upper arm or thigh)	≥ 50% surface area of the extremity segment involved (eg, upper arm or thigh) OR Phlebitis OR Sterile abscess	Potentially life- threatening consequences (eg, abscess, exfoliative dermatitis, necrosis involving dermis or deeper tissue) OR Hospitalization indicated
Injection Site Induration or Swelling Report only one > 15 years of age	Same as for Injection Site Erythema or Redness, > 15 years of age	Same as for Injection Site Erythema or Redness, > 15 years of age	Same as for Injection Site Erythema or Redness, > 15 years of age	Same as for Injection Site Erythema or Redness, > 15 years of age

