\leq 15 years of age	Same as for Injection Site Erythema or Redness, ≤15 years of age	Same as for Injection Site Erythema or Redness, ≤15 years of age	Same as for Injection Site Erythema or Redness , ≤ 15 years of age	Same as for Injection Site Erythema or Redness , ≤ 15 years of age
Injection Site Pruritus	Itching localized to the injection site that is relieved spontaneously or in < 48 hours of treatment	Itching beyond the injection site that is not generalized OR Itching localized to the injection site requiring \geq 48 hours treatment	Generalized itching causing inability to perform usual social & functional activities	NA

Injection Site Erythema or Redness should be evaluated and graded using the greatest single diameter or measured surface area.

Laboratory Values* Chemistries

Parameter	Grade 1 Mild	Grade 2 Moderate	Grade 3 Severe	Grade 4 Potentially Life- Threatening
Acidosis	NA	pH ≥ 7.3 to < LLN	pH < 7.3 without life-threatening consequences	pH < 7.3 with life- threatening consequences
Albumin, Low (g/dL; g/L)	3.0 to < LLN 30 to < LLN	\geq 2.0 to < 3.0 \geq 20 to < 30	< 2.0 < 20	NA
Alkaline Phosphatase, High	1.25 to < 2.5 x ULN	2.5 to < 5.0 x ULN	5.0 to < 10.0 x ULN	\geq 10.0 x ULN
Alkalosis	NA	$pH > ULN \text{ to } \le 7.5$	pH > 7.5 without life-threatening consequences	pH > 7.5 with life- threatening consequences
ALT or SGPT, High Report only one	1.25 to < 2.5 x ULN	2.5 to < 5.0 x ULN	5.0 to < 10.0 x ULN	≥ 10.0 x ULN
Amylase (Pancreatic) or Amylase (Total), High Report only one	1.1 to < 1.5 x ULN	1.5 to < 3.0 x ULN	3.0 to < 5.0 x ULN	\geq 5.0 x ULN
AST or SGOT, High Report only one	1.25 to < 2.5 x ULN	2.5 to < 5.0 x ULN	5.0 to < 10.0 x ULN	\geq 10.0 x ULN
Bicarbonate, Low (mEq/L; mmol/L)	16.0 to < LLN 16.0 to < LLN	11.0 to < 16.0 11.0 to < 16.0	8.0 to < 11.0 8.0 to < 11.0	< 8.0 < 8.0
Bilirubin Direct Bilirubin ¹ , High > 28 days of age	NA	NA	> ULN with other signs and symptoms of hepatotoxicity.	> ULN with life- threatening consequences (eg, signs and symptoms of liver failure)
Total Bilirubin, High > 28 days of age	1.1 to < 1.6 x ULN	1.6 to < 2.6 x ULN	2.6 to < 5.0 x ULN	\geq 5.0 x ULN

*Reminder: An asymptomatic abnormal laboratory finding without an accompanying AE should not be reported to DAIDS in an expedited time frame unless it meets protocol-specific reporting requirements.

¹ Direct bilirubin > 1.5 mg/dL in a participant < 28 days of age should be graded as grade 2, if < 10% of the total bilirubin.

CONFIDENTIAL

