10.2.1 Injection Area Symptoms

The proportion of participants reporting each injection area symptom will be presented by treatment group for the safety population. For each injection area symptom, the determination of whether or not the specific symptom occurred on each day and 'Any Day 1 to 7' will be made.

For the 'Any Day 1 to 7' summary tables, the derivation of the proportion is calculated as n1/(n1+n2) where

- n1: Any Day 1 to 7 participant reports the symptom as 'mild', 'moderate' or 'severe' on any Day 1 to 7.
- n2: Participant reports the symptom as 'none' on all 7 days or as a combination of 'none' and missing on all 7 days.

Participants that report the symptom as missing on all 7 days are not included in the proportion calculations.

For redness and swelling, 'mild', 'moderate', and 'severe' categories are based on the largest diameter of the redness or swelling reported in mm and they are age-group specific:

- for participants >15 years: Mild 25 to <50mm; Moderate >=50 to <100 mm; Severe >=100 mm;
- for participants <=15 years: Mild 0 to <=25mm; Moderate >25 to <50 mm; Severe >=50 mm

(refer to the 'Site Reactions to Injections and Infusions' table in Appendix 5 of the study protocol which is based on the Division of AIDS Table for Grading the Intensity [severity] of Adult and Pediatric Adverse Events Version 2.1, July 2017). For participants > 15 years old, 'none' = largest diameter reported on the diary card<25 mm.

95% CI based on the conditional binomial Clopper-Pearson method with mid-p correction (refer to Appendix 7) will be provided.

The maximum severity (highest grading) of each local reaction within 7 days of vaccination will be derived as follows:

- =., if values are missing for all Days 1 to 7.
- =0, if the participant reports all reactions as 'None' or a combination of missing and none for all Day 1 to 7.
- =highest grade (maximum reported severity) within 7 days of vaccination if the answer is not 'None' for at least 1 day.

Results will be summarized for each local reaction reporting n (%) participants by maximum severity within each age group (>15 years and <=15 years).

Duration and Onset Day of Injection Area Symptom:

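### SAP 10.2.1 cites protocol Appendix 5 for its diary redness and swelling grades, but three of its diameter limits differ from the current table and the difference is not declared

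*SAP*

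**What the plan says.** SAP 10.2.1 says that for redness and swelling the "categories are based on the largest diameter of the redness or swelling reported in mm", with limits that depend on age. For participants aged 15 or younger: "for participants <=15 years: Mild 0 to <=25mm; Moderate >25 to <50 mm; Severe >=50 mm". For those older than 15, Mild runs from 25 to below 50 mm, Moderate from 50 to below 100 mm, and Severe from 100 mm. It adds: "For participants > 15 years old, 'none' = largest diameter reported on the diary card<25 mm". No diameter for none is given for the younger group. The section refers the reader to the site-reactions table in protocol Appendix 5 for these limits, and SAP Section 2 states that the SAP is based on Protocol Version 7.

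The current table in protocol Section 10.5 (Appendix 5) reads as follows for redness:
- Older than 15, Grade 1: "2.1 to < 5 cm in diameter". Grade 2 starts at 5 cm and Grade 3 at 10 cm.
- 15 or younger, Grade 1: "2.1 cm to ≤ 2.5 cm in diameter".
- 15 or younger, Grade 2: "> 2.5 cm in diameter with < 50% surface area of the extremity segment involved (eg, upper arm or thigh".
- 15 or younger, Grade 3: "≥ 50% surface area of the extremity segment involved (eg, upper arm or thigh", or phlebitis, or sterile abscess.

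For induration or swelling the entry is "Same as for Injection Site Erythema or Redness, ≤15 years of age", with a matching entry for the older group.

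SAP Section 6 lists one change from the protocol, the removal of the ITT population.

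**The concern.** A reader of the reactogenicity tables would take Severe at 15 or younger to mean Appendix 5 Grade 3. It does not. The diary (SAP 10.2) records the largest diameter, not the share of the extremity segment, so 50 mm can only be a proxy, and the SAP does not call it one.

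The lower limits raise a second problem. The proportion for any reaction on Days 1 to 7 is n1/(n1+n2), where n1 counts participants graded mild, moderate or severe. It is presented by treatment group with no stated split by age. Younger participants would enter n1 at any recorded diameter and older ones only from 25 mm, so the pooled rate has no single definition of a reaction.

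Solicited AEs through 7 days are a secondary safety endpoint (Protocol Section 3, SAP Section 3), and injection area symptoms by maximum severity also go to the IDMC (SAP 4.2.3).

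**Working it through.** **Inputs.** SAP limits from 10.2.1; protocol limits from Appendix 5, converted from cm to mm. Only size criteria were compared; symptoms, phlebitis and abscess were left out.

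**Step 1. Limits side by side.**

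| Limit | SAP 10.2.1 | Appendix 5 | Match |
|---|---|---|---|
| >15, start of Mild / Grade 1 | 25 mm | 21 mm | no |
| >15, start of Moderate / Grade 2 | 50 mm | 50 mm | yes |
| >15, start of Severe / Grade 3 | 100 mm | 100 mm | yes |
| ≤15, start of Mild / Grade 1 | 0 mm | 21 mm | no |
| ≤15, top of Mild / Grade 1 | 25 mm | 25 mm | yes |
| ≤15, start of Severe / Grade 3 | 50 mm diameter | 50% of segment surface | no |

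Three of the six limits differ.

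**Step 2. What 50 mm means as an area.** Treat the reaction as a circle.
- Area at 50 mm = π × 2.5² = 19.6 cm².
- It covers half the segment only if the whole segment is at most 2 × 19.63 = 39.3 cm².

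The documents give no segment area. Assume S between 200 and 900 cm²:
- Share covered by a 50 mm circle: 19.63/200 = 9.8%, down to 19.63/900 = 2.2%.
- Diameter in mm at which a circle covers half the segment = 20 × √(S/2π). For S = 200 this is 113 mm; for S = 900 it is 239 mm.

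**Step 3. Diameters at which the two gradings disagree** (each whole mm from 0 to 300 graded under both rules).
- Older than 15: 21–24 mm only.
- 15 or younger: 0–20 mm, and again from 50 mm up to 112 mm (S = 200), 159 mm (S = 400), 195 mm (S = 600) or 239 mm (S = 900).

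**Step 4. Examples.**

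| Diameter | SAP, age 15 | SAP, age 16 | Appendix 5, both ages |
|---|---|---|---|
| 10 mm | Mild | none | below Grade 1 |
| 22 mm | Mild | none | Grade 1 |
| 50 mm | Severe | Moderate | Grade 2 |

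The Grade 2 entry at age 15 holds for any segment larger than 39.3 cm².

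**Step 5. A cross-check inside the SAP.** SAP 10.5 takes redness, swelling or induration above 20 mm at the site examination as an AE, at every age. That is a separate record from the diary, but its line agrees with the 2.1 cm start in Appendix 5 and not with either lower limit in 10.2.1.

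**The case against.** The strongest reply is that little depends on this. The same rules apply in both arms, so the comparison between arms is not biased. The summaries are descriptive. Maximum severity is already reported separately on each side of age 15. At 15 or younger the 50 mm rule errs towards over-calling Severe, which is the cautious direction in a safety table. Investigators also grade AEs on the eCRF by the DAIDS table, and pausing rule 3 rests on investigator judgement, not on these diary categories. All of this stands and limits the consequence. It does not make the categories agree with the table they cite, and the absolute rates and severities are themselves the reported result.

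A footnote to Appendix 5 allows redness to be graded by greatest single diameter or by measured area, so grading by diameter is not wrong in itself. That is fair, but the footnote supplies no millimetre limit for Grade 3 at 15 or younger.

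A diary answer of none would probably cover a 0 mm reading in the younger group. That narrows the gap at the bottom to 1–20 mm without closing it.

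Two of the three limits resemble the superseded table in the protocol's version history (2.5 cm start above 15; no lower limit at 15 or younger). Carry-over is therefore a plausible explanation, though an inference. The 50 mm boundary matches neither table.

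Finally, the diary card is not among the documents, so any bands printed on it cannot be checked. The mismatch in the text is certain; its effect on the counts is not.

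**Conclusion.** The point holds. SAP 10.2.1 departs from its cited source at three limits: the Grade 1 start in each age group, and the Grade 3 boundary at 15 or younger. Section 6 declares none of them. Followed as written, the plan would grade some reactions differently from Appendix 5 and give the pooled any-reaction proportion two definitions by age. The bands of disagreement below 25 mm come straight from the two texts. The upper end of the band above 50 mm rests on a circular reaction and an assumed segment area. How many participants fall in these bands cannot be derived. No effect on efficacy or on the pausing rules is shown. This should be fixed before the safety tables are produced.

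**What to change.** Reconcile SAP 10.2.1 with the current Appendix 5:
- Use the table's Grade 1 lower limit (2.1 cm) in both age groups, and state the diameter that counts as none at 15 or younger.
- Do not label 50 mm or more at 15 or younger as Appendix 5 Severe. Either report diameters above 25 mm in that group as Grade 2 or higher by diameter, or keep a diameter proxy for Grade 3 that is labelled as a proxy.
- Declare in SAP Section 6 any limit that still differs from the protocol, including such a proxy.

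The cost is SAP wording and table programming, with no new data. The drawback is that diary diameter alone cannot separate Grade 2 from Grade 3 at 15 or younger, so that split is either not shown from the diary or rests on a declared proxy.

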10.2.2 General Body Symptoms

For each general body symptom event recorded on the diary, the following summaries and analyses will be presented similarly to injection area symptoms:

- Each general body symptom on each day (up to Day 7) after vaccination
- Each general body symptom event on 'Any Day 1 to 7' after vaccination
- Maximum severity of each general body symptom event on 'Any Day 1 to 7' after vaccination
- Maximum duration of each general body symptom after vaccination
- Any general body symptom event (including fever) on 'Any Day 1 to 7' after vaccination

Grading for fever is as follows: Mild=38.0 to <38.6°; Moderate>=38.6 to <39.3°C; Severe>=39.3 to <40.0°C; Life-threatening>=40°C. The derivation of these variables is similar to the derivation of the variables for injection area symptoms.

10.3 Use of Medication

The use of medication will be recorded on the Diary Card for 7 days after vaccination.

The following variable will be derived:

• Use of medication on 'Any Day 1 to 7' after vaccination

10.4 Diary Card Completion

The number of participants who returned the diary card, including the reason for not returning the diary card will also be summarized. For any given day, the diary will be considered as complete if all expected data (the 3 injection area symptoms, the 4 general body symptom events, and the use of medication for the 7 days) are available (i.e. a non-missing response is available). If any of the items in the diary is missing on a specific day, the diary is considered as incomplete.

The following diary compliance variables will be derived as follows and presented by treatment group:

- Compliance per day: the numerator is the number of participants who completed the diary on a given day (Day 1 to Day 7) and the denominator is the total number of participants who receive the vaccination.
- Compliance at least x days for x = 1, 2,7: the numerator is the number of participants who completed the diary on any x days, and the denominator is the total number of participants who received the vaccination.

10.5 Injection Site Examination

Injection site reaction assessments are recorded at Day 8, Day 29, Day 71, and Month 6 (refer to Protocol Section 8.2.6) and will be summarized for the Safety population. A corresponding listing will be presented for the Safety population.

In addition to the scheduled time points, an 'Any Time Point' will be derived. This will be defined as the worst case result per assessment and participant. Worst case assessment is defined as the largest measurement (mm) for assessments with measurements or the presence of the reaction if 0 measurements are available.

The presence and maximum diameter of injection site reactions will be recorded as follows:

- redness, swelling, or induration <=20 mm is considered as anticipated
- redness, swelling, or induration >20 mm is reported as an AE
- papule, vesicle, pustule, ulcer, or scar <=5 mm is considered as anticipated
- papule, vesicle, pustule, ulcer, or scar >5 mm is reported as an AE.

10.6 Clinical Laboratory Assessments

Clinical laboratory assessments including hematology, serum chemistry, urinalysis, a human immunodeficiency virus (HIV) test and a serum pregnancy test (females only) will be measured at Screening. HIV testing is repeated yearly.

Hematology	Complete blood count (hematocrit, hemoglobin, platelets, and white blood cells) and absolute counts for neutrophils, lymphocytes, basophils, eosinophils, and monocytes
Serum chemistry	Alanine aminotransferase (ALT), aspartate aminotransferase (AST), alkaline phosphatase, total bilirubin, creatinine, blood urea nitrogen (BUN), potassium, sodium.
Urinalysis	Specific gravity, pH, glucose, protein, blood, ketones, bilirubin, urobilinogen, nitrite, leukocyte esterase by dipstick

Descriptive statistics (based on Systeme Internationale [SI] units) for laboratory parameters will be presented at Screening by treatment group.

HIV testing results will be presented by yearly visits, as per time and event schedule.

The laboratory values will be graded programmatically by using the grading criteria in the Protocol Appendix 5: Toxicity table. The number and proportion of participants will be summarized by grading category and treatment group.

Detailed participant listings of all laboratory data collected during the study will be provided. Laboratory values outside normal limits will be identified in a participant data listing. A column will display any applicable toxicity grading of the laboratory value.

10.7 Vital Signs and Weight

Vital signs, including blood pressure, pulse rate, respiratory rate, and body temperature, will be collected at Screening and Day 1 (pre vaccination). These will be presented in a listing for the Safety population.

Height and weight will be measured at Screening, Day 1, and every 6 months thereafter. The results (including change from baseline for height, weight, and BMI) will be included in a by-participant listing and summarized at each visit by treatment group for Safety population.

10.8 Physical Examination

Findings from physical examinations will be presented in listings for the Safety population. Focused physical examination will be collected throughout the study and will be summarized descriptively by treatment group and by visit. Summary results will include the number and percentage of participants with clinically and non-clinically significant results at each visit.

10.9 Signs and Symptoms of TB

Tuberculosis symptom screen results at each visit and overall clinical TB diagnosis will be included in a by-participant listing for Safety population.

The following will be reported overall during the study by treatment arm for Safety and mITT for efficacy populations:

- Number of suspected TB diagnoses (events) by treatment group (across all participants withing each treatment group).
- Rate of reported TB symptoms (events) reported for all suspected TB diagnoses (events) by treatment group (across all participants withing each treatment group). The analysis will be based on the number of events and a participant may have more than one event throughout the study.
- Rate of referral to the National TB Programme for treatment (based on a 'yes' response from the following question on the eCRF: 'Was the participant referred to the National TB program for treatment?') events based on suspected TB diagnoses (events).

• The incidence rate of confirmed TB cases defined as bacteriologically-confirmed TB (Positive culture result [Mycobacterium tuberculosis positive] or positive GeneXpert result [MTB detected]) cases. The incidence rate will be calculated using the number of bacteriologically confirmed TB cases across all visits as the numerator and the duration of follow-up (in months) as the denominator. For participants with bacteriologically confirmed TB, the duration of follow-up will be from the randomization date up to the visit date when case is confirmed. For all other participants, the duration for follow-up will be calculated from the randomization date up to the study completion or early discontinuation date.

The following will be reported by calendar month (as reflected in study visit date) and by treatment group for Safety and mITT for efficacy populations:

- Number and percentage of participants who were diagnosed with suspected TB (yes/no) with percentages calculated based on number of participants still in the study in the respective calendar month.
- Number and percentage of participants with bacteriologically-confirmed TB (Positive culture result [Mycobacterium tuberculosis positive] or positive GeneXpert result [MTB detected]).

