7.2. Participant Discontinuation/Withdrawal from the Study

A participant may withdraw (or a participant's parent or guardian (a guardian is a legally acceptable representative [LAR]) may withdraw the participant) from the study at any time or may be withdrawn at any time at the discretion of the investigator for safety, behavioral, compliance, or administrative reasons. This is expected to be uncommon.

If possible, a discontinuation visit should be scheduled for any participant who wishes to discontinue or withdraw from the study. At this visit, topics around subject safety as well as the use of already collected biospecimens will be discussed.

The time and reason for withdrawal should be noted in the space provided for this purpose in the CRF. Participants who are withdrawn because of occurrence of AE should be clearly distinguished from participants who are withdrawn for other reasons. Participants who are withdrawn will be followed up for an AE until the event resolves or stabilizes.

Refer to Appendix 1, Section 10.1.4 regarding the informed consent process.

If a participant withdraws from the study, he/she may request destruction of any samples taken and not tested, and the investigator must document this in the site study records and the CRF.

A participant may, at the investigator's discretion, be withdrawn from the study if any one of the below conditions apply. If not withdrawn, participants with the below conditions will be followed as described in the protocol, including all required blood draws.

- Development of active TB or receipt of curative anti-tuberculous therapy
- Development of autoimmune disease or immunosuppression, or an AE of special interest
- Receipt of investigational drug therapy or investigational vaccine (other than study injection)

No replacements are planned for the withdrawals in the study.

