5 STUDY POPULATIONS

5.1 Analysis Populations

Sponsor authorization of the assigned analysis populations is required for the primary analysis, the secondary analysis (after all participants have at least 36 months of follow-up/have discontinued early), and for the final analysis. Agreement and authorization of participants included/excluded from the Per Protocol (PP) population for the primary analysis will be obtained prior to any unblinding activities. Reason(s) for exclusion from the PP population will be applied consistently across all participants with detailed documentation.

	Description
Enrolled population	All participants who provide informed consent.
Randomized population	All participants randomly assigned to study intervention. A participant will be programmatically included in this analysis population if the participant has a randomization number and date of randomization. Participants will be analyzed according to the intervention they were randomized to.
Modified intention to treat (mITT) efficacy population	All participants randomly assigned to study intervention who received the study intervention, and are QFT negative at the Day 71 visit, or at the first study visit post Day 71 for which a QFT result is available if the Day 71 study visit was missed or the Day 71 QFT result was not available [1]. Participants will be analyzed according to the intervention they were randomized to.
Per Protocol (PP) efficacy population	All participants in the mITT population who did not substantially deviate from the protocol procedures and who received the treatment to which they were randomized. Participants who substantially deviated will be identified prior to database lock and unblinding [2]. Participants will be analyzed according to the intervention they were randomized to.
Safety	All participants randomly assigned to study intervention who received the study intervention. Participants will be analyzed according to the intervention they received.

[1] Because of COVID-19, many study participants enrolled less than 70 days prior to the enrollment pause on 19 March 2020, may have missed their Day 71 visit. Participants who missed Day 71 visit are eligible for inclusion in the mITT population if their first QFT result post randomization is negative and are excluded from the mITT population if their first QFT result post randomization is not negative.

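### The mITT incidence rate of confirmed TB counts person-time from randomisation, before anyone can qualify for mITT, and so understates the absolute rate by about 5%

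*SAP*

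**What the plan says.** SAP 10.9 opens its list of overall TB summaries with "The following will be reported overall during the study by treatment arm for Safety and mITT for efficacy populations". One of these is the incidence rate of bacteriologically confirmed TB, which takes the "number of bacteriologically confirmed TB cases across all visits as the numerator and the duration of follow-up (in months) as the denominator".

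The same section gives two follow-up rules, and both start at randomisation:

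- Participants with confirmed TB: "the duration of follow-up will be from the randomization date up to the visit date when case is confirmed".
- Everyone else: "the duration for follow-up will be calculated from the randomization date up to the study completion or early discontinuation date".

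No separate rule is given for mITT. SAP 5.1 restricts mITT to randomised and injected participants who "are QFT negative at the Day 71 visit, or at the first study visit post Day 71 for which a QFT result is available". SAP 9.1 measures event and censoring times for sustained conversion from Day 71 (or its replacement visit) and uses the total of those times as the denominator of the sustained-conversion incidence rate.

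**The concern.** A person-time rate should count time only while a participant could contribute a case to the population being described. In mITT, membership is decided by a test at least 70 days after randomisation. Someone who develops TB before that test and is QFT-positive at it is removed. So is someone withdrawn for TB before having any post-randomisation QFT result; Protocol 7.2 leaves such withdrawal to the investigator. Everyone who passes the test brings its waiting time into the denominator. That time is selected for having few cases, and it dilutes the rate.

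The report would also carry two mITT incidence rates with different time origins, one for sustained conversion and one for TB, with no reason given for the difference.

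What is at stake is the absolute TB rate in mITT. SAP Section 3 lists incidence of laboratory-confirmed TB among the exploratory endpoints, and Protocol 2.1 says the trial is meant to inform whether a prevention-of-disease trial is justified. A reader may therefore take the rate at face value.

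**Working it through.** The documents state no TB rate, expected TB case count or person-time total, so there is no plan figure to reproduce. The check sizes the dilution.

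**Inputs**

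- Time before qualification: 70 days (SAP 4.1), or 70 × 12/365.25 = 2.30 months. It is longer where Day 71 was missed; Protocol 7.4.5 expects this for most participants enrolled less than 70 days before the March 2020 pause.
- Planned follow-up: 48 months (Protocol 4.3), 1461 days.
- Loss to follow-up: 5% per year; 900 per arm; 7% ineligible for mITT at Day 71 (Protocol 9.2). This gives 900 × 0.93 = 837 per arm in mITT.
- TB rate, for illustration only: 0.22 per 100 person-years in QFT-negative adolescents (Protocol Section 2).

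**Share of mITT person-time before qualification, s**

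With no loss, s = start/48 months. With loss, h = −ln(0.95)/12 per month, mean follow-up = start + (1 − e^(−h(48 − start)))/h, and s = start/mean follow-up.

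| Qualifying QFT | s, no loss | s, 5% per year loss | Factor on the rate if corrected, 1/(1 − s) |
|---|---|---|---|
| Day 71 (2.30 months) | 70/1461 = 4.8% | 2.30/43.81 = 5.2% | 1.05 to 1.06 |
| Month 6 | 6/48 = 12.5% | 6/44.45 = 13.5% | 1.14 to 1.16 |
| Month 12 | 12/48 = 25% | 12/45.37 = 26% | 1.33 to 1.36 |

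The Month 6 and Month 12 rows describe a participant who qualifies that late, not the cohort. As a rough cohort figure, suppose all 349 participants on study at the pause (Protocol 7.4.1), out of 1800, qualified only at Month 6 and the rest at Day 71. The average share would then be 349/1800 × 12.5% + 1451/1800 × 4.8% = 2.4% + 3.9% = 6.3%. The documents do not say how many qualified late.

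**In person-years, per arm**

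- From randomisation: 837 × 43.81/12 ≈ 3,056.
- From Day 71: ≈ 2,896.
- At 0.22 per 100 person-years after Day 71: 0.0022 × 2,896 = 6.37 cases.
- Rate as planned: 6.37/3,056 = 0.21 per 100 person-years.

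**Allowing for cases before qualification**

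Let k be the rate among eventual qualifiers before the test, divided by their rate after it. Then planned rate/corrected rate = (1 − s) + s × k. With s = 4.8%, k = 0 gives 0.952 and k = 1 gives 1.000. The 4.8% is therefore the full dilution when no counted case falls in the period; any such case reduces it.

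**Between arms**

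With similar follow-up, s is similar in both arms and cancels from the rate ratio.

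**Safety population**

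Randomisation and injection are both on Day 1, and no later test is required. There is no time before qualification and no effect.

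**The case against.** The best defence is that cases and person-time both start at randomisation, and that mITT exclusion depends on QFT status, not on TB. Participants excluded at the test leave the numerator and the denominator together. A participant with confirmed TB in the first 70 days who is QFT-negative at the test stays in mITT and is counted, and TB surveillance covers that period. It follows that a reader who infers that the wash-out is case-free by construction goes too far. The defence does not remove the point: the test selectively removes early cases who are positive, and every qualifier's waiting time stays in.

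A reader might also infer that the rate double-counts, because the numerator takes cases across all visits while person-time stops at confirmation. The sentence that seems to support this, "The analysis will be based on the number of events and a participant may have more than one event throughout the study", belongs to the bullet on TB symptoms among suspected diagnoses. The confirmed-case bullet splits participants into those with and without confirmed TB and refers to a single confirming visit. The natural reading is a first-case rate, in which numerator and denominator match.

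What remains is missing wording. First case per participant is not stated, and follow-up can continue after TB: "If not withdrawn, participants with the below conditions will be followed as described in the protocol, including all required blood draws" (Protocol 7.2). If repeats were counted, one among an assumed six first cases would raise an arm's rate by 1/6 = 17%. The documents give no frequency for repeats, so this is not a finding about the plan.

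Finally, this is not the only view of TB by arm. SAP 10.9 also tabulates participants with confirmed TB by calendar month and provides a by-participant listing.

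**Conclusion.** The time-origin point holds for mITT. Following SAP 10.9 as written understates the absolute mITT rate of confirmed TB by about 5%, and by about 12.5% for the contribution of a participant qualifying at Month 6. These figures assume 48 months of follow-up and no counted cases before qualification; 5% yearly loss raises them slightly, to 5.2% and 13.5%.

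The documents do not support a claim that the comparison between arms is biased: the dilution is similar in both and the rate ratio barely changes. The Safety rate is correct as defined. The rate is a descriptive summary for an exploratory objective with no test attached, so no primary or secondary conclusion is touched. Low priority.

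**What to change.** In SAP 10.9, add a rule for mITT: person-time and case counting for the TB rate both start at the date of the qualifying negative QFT (Day 71 or the first later result). Keep the randomisation start for the Safety population.

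As a clarification, state that the numerator is participants with a first bacteriologically confirmed case, which matches the existing end of person-time at confirmation, and list any later episodes separately.

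The cost is two sentences and a small derivation change, with no new data. There is one small loss: a case confirmed before qualification in a participant who then tests QFT-negative would appear only in the Safety rate and the listing. The SAP should say so, and say that such a participant contributes neither a case nor person-time to the mITT TB rate.
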